- 1) Participants with a unilateral transtibial (below-knee) amputation (up to 40) will be fit with our motor-driven and computer controlled **torsionally adaptive prosthesis (TAP)**. The TAP can pair turning and flexing motion at different proportional settings; several paired motion ratio settings of turning (transverse plane motion) to flexing (sagittal plane motion) will be tested. Over two visits, participants will do a series of walking tests over level ground with the TAP set at different pairing settings (blinded and random order) while biomechanical data is collected. Satisfaction data will be collected for each setting. The results will be used to inform the design of the PFF.

Based on results from the TAP testing, we will design and build PFFs of various sizes and stiffnesses to compare to a standard-of-care prosthesis. In a blinded crossover experiment, over 3 visits, participants (up to 40) will be fit with the study prostheses (PFF or a standard-of-care prosthetic foot) in random order and wear each study prosthesis at home for 2 weeks. Participants will visit the laboratory to do a series of walking tests after each 2-week acclimation period.

List of Abbreviations

AE – adverse event

CPRS - Computerized Patient Record System

CRQ – Continuing Review Questionnaire

HIPAA – Health Insurance Portability and Accountability Act

ISO - Information Security Officer

IRB – institutional review board

PFF – Pivot-Flex Foot

PHI – protected health information

PI – Principal Investigator

PO – Privacy Officer

ROP – report of other problem

SA – specific aim

SAE – serious adverse event

SD – standard deviation

TAP – torsionally adaptive prosthesis

TT – transtibial

UW – University of Washington

VA – Veterans Affairs

Contents

Protocol Title: Pivot-Flex Foot

1.0	Key Study Personnel.....	5
2.0	Introduction.....	5
3.0	Specific Aims and Hypotheses.....	6
4.0	Resources and Personnel.....	6
5.0	Study Procedures.....	6
5.1	Study Design.....	7
5.2	Recruitment Methods and Initial Screening.....	7
5.3	Informed Consent Procedures.....	10
5.4	Inclusion/Exclusion Criteria.....	11
5.5	Study Visits, Data Collection, and Risk Management.....	11
5.6	Data Analysis.....	18
5.7	Withdrawal of Subjects.....	21
6.0	Reporting.....	21
7.0	Information Security, Privacy, and Confidentiality.....	211
8.0	Communication Plan.....	22
9.0	References.....	23

Protocol Title: Pivot-Flex Foot

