- Prosthesis information (socket, liner, suspension, and foot type, category, and/or size

Self-Selected Walking Speed (SSWS) Tests

Participants will use their own prosthesis during these tests. Participants will be asked to walk several times, at their self-selected pace, for about 65-feet back and forth in a straight hallway. Participants will also be asked to walk at their own pace several times around a ~3-foot radius circle. These tests will be used to determine each participants' straight line and circle SSWS.

Randomization to Study Prosthesis – At Home Acclimation

Participants will be randomized to wear the PFF or the standard-of-care prosthetic foot for the next 2 weeks at home/in the community during their normal daily activities. The research prosthetist will fit the PFF or standard-of-care foot to the participants as-prescribed socket and suspension system. Participants will be blinded to prosthetic foot type. The prosthetic feet will be covered with a sock and cosmesis and participants will be instructed not to remove the coverings from the foot. Participants will practice walking on the assigned foot until they feel confident/stable. If confidence and stability cannot be achieved the participant may not be able to continue in study. Participants will be instructed to contact us if they have any problems or concerns with the study prosthesis during the 2-week acclimation period. We will arrange to make prosthetic adjustments if needed. We will store the participants' prescribed prosthetic foot during the at-home acclimation periods.

Visit 2

After wearing the study prosthesis for approximately 2-weeks participants will return to the lab to do a series of walking tests.

Motion and Force Measurement

Participants will be asked to change into a tight-fitting shirt and shorts that we provide. A private changing area will be provided. We will record a series of standard body measurements such as height, weight, and leg length. We will attach up to 70 small reflective markers with double sided tape to specific locations on the participants' hands, trunk, legs, and feet.

During the walking tests in the lab, the infrared cameras will record the location and movement of the markers; they do not record a picture of the body. Data will also be collected by force plates embedded in the floor of the lab; participants will walk across and stand on the plates during the tests.

SSWS Walking Tests

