While using the study prosthesis, participants will be asked to walk back and forth in a straight line several (approximately 3-6) times at their SSWS. Participants will also be asked to walk around a ~3-foot radius circle several (3-6) times at their SSWS. They will be asked to do the circle walking tests in both clockwise and counter-clockwise directions (randomized order).

Study Prosthesis – At Home Acclimation

The research prosthetist will fit participants with the other study prosthesis. Participants will remain blinded to the foot type. Participants will practice walking on the assigned foot until they feel confident/stable. If confidence and stability cannot be achieved the participant may not be able to continue in study. Participants will be instructed to contact us if they have any problems or concerns with the study prosthesis during the 2-week acclimation period. We will arrange to make prosthetic adjustments if needed.

Visit 3

After wearing the study prosthesis for approximately 2-weeks participants will again return to the lab to do a series of walking tests. The Motion and Force Measurement, and SSWS Walking Tests described in Visit 2 will be repeated. The research prosthetist will re-fit participants with their as-prescribed prosthetic foot.

Applicable to Parts 1 & 2

During study sessions, visitors and observers will not be allowed in the lab unless the participant agrees to their presence; the participant can change her/his mind at any time.

Photos and video

We may take video and photos of participants during portions of this study for documentation and use in research publications. To protect the identity and privacy of our participants, all videos and photos will be edited later to de-identify the images (e.g., bluring of faces, tattoos, and other distinguishing marks). No sound will be recorded to prevent voice identification.

Repository

Participants will be asked if they are interested in allowing their study data to be added to our de-identified data repository so that it may be used for additional research in the future. Participants who are interested will be asked to sign a separate consent form for the repository (MIRB# 00493). Once the consent form is signed, a copy of the data will be added to the repository on an ongoing basis throughout the course of the study.

Payment to Participants

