In part 2 of the study, we may discover that participants have peripheral neuropathy with impaired sensation in their residual limb, or that the level of neuropathy or impaired sensation is different than participants were aware of. This may cause some level of stress. For dysvascular individuals, it is not uncommon for the residual lower-limb to have some level of

peripheral neuropathy with impairment of sensation. Semmes-Weinstein monofilament testing is a simple and non-invasive test normally administered to dysvascular patients to assess protective sensation on the level of the skin of the lower extremities. The selected monofilament test score threshold should minimize the risk of dysvascular participants being unable to notice skin irritation on their residual limb. If participants become distressed during the Semmes-Weinstein monofilament testing we will advise them to see their regular care provider.

The tape used to apply the markers may cause mild skin discomfort or irritation while worn or when removed (feels similar to removing a band-aid). Only trained study staff will place and remove the reflective markers. Participants may feel embarrassed while wearing the tight fitting clothing.

It is also possible that participants may experience stress or inconvenience by coming to the VA for multiple visits. Participants can stop their participation at any time.

The PI will ensure the study procedures are being properly followed by keeping the research staff well informed of the current study procedures through regular/ongoing contact. Although an injurious fall or a prosthetic component failure related to this protocol is unlikely, we will tabulate a list of any such reports that occur during the study and compare it with corresponding data available in the literature. This will allow us to analyze how much of an increased risk was due to the administered protocol. After each report of an AE, SAE or an unanticipated problem, we will evaluate study procedures for previously-assessed risks, and will determine whether any changes to the protocol are necessary to minimize risks. The study will be suspended until these changes have been fully implemented and approved by the IRB.

Privacy and Confidentiality

See section 7.0 below for Information Security, Privacy, and Confidentiality related procedures.

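### Falls and component failures are to be compared only with published data; no by-foot safety table is planned, although Part 2 gives each participant a randomised standard-of-care period of about equal length

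*Protocol*

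**What the plan says.** The safety method is in Protocol section 5.5, under Risks and Risk Management. After calling injurious falls and component failures unlikely, the protocol says "we will tabulate a list of any such reports that occur during the study" and that the team will "compare it with corresponding data available in the literature". The stated purpose follows: "This will allow us to analyze how much of an increased risk was due to the administered protocol". No split by study part, device or foot is given, and exposure time is not mentioned.

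The design of Part 2 is in the Abstract (Methodology) and in section 5.5. The Abstract says "participants (up to 40) will be fit with the study prostheses (PFF or a standard-of-care prosthetic foot) in random order", and that they will "wear each study prosthesis at home for 2 weeks". At Visit 1, "Participants will be randomized to wear the PFF or the standard-of-care prosthetic foot for the next 2 weeks at home/in the community". At Visit 2, "The research prosthetist will fit participants with the other study prosthesis", again for about two weeks. Participants are blinded to foot type in both periods.

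No other part of the documents supplies a by-foot safety comparison:
- Section 5.6 compares the two feet on peak transverse-plane moment and positive hip work only.
- Section 6.0 covers how safety information is collected and reported.
- The SAP covers outcomes by coupling ratio (Part 1) and contains no safety analysis and no PFF versus standard-of-care analysis.

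**The concern.** The PFF is a new device, built within the study and worn at home. The protocol itself gives reasons to ask about it separately. The Introduction notes that torsion adapters that are too compliant may reduce gait stability. Section 5.5 singles out the TAP and the PFF for bench testing, and describes the comparator as a common commercial foot.

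A comparison with published data has no concurrent control. An apparent excess could come from the PFF, from getting used to any unfamiliar foot, from a different case mix, from closer event reporting, or from a different definition of a fall. An apparent absence of excess could conceal offsetting differences. The randomised standard-of-care period holds the participants, definitions, reporting route and newness of the foot constant, and the plan does not say it will be used for safety. At stake is whether the trial can report an event rate for the PFF beside that of its own comparator.

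**Working it through.** The documents give no event rate, expected count, margin or power for falls or component failures, so there is no stated figure to reproduce. The checks below show what each comparison can and cannot tell.

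**1. Exposure (Abstract; section 5.5, Part 2).** Up to 40 participants, about 2 weeks on each foot.
- 40 × 2 = 80 person-weeks per foot, or 80 × 7 / 365.25 = 1.53 person-years.
- With 15 completers (the number in the section 5.6 power statement), 15 × 2 = 30 person-weeks per foot.

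**2. What a total over both feet shows.** Assume equal exposure and a standard-of-care risk equal to the published risk. If the PFF multiplies risk by RR, the ratio of the Part 2 total to the literature expectation is (1 + RR) / 2.
- RR = 2: (1 + 2) / 2 = 1.5.
- RR = 3: (1 + 3) / 2 = 2.0.

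Now let the PFF add nothing, but let both feet carry 1.5 times the published risk because they are unfamiliar or because the population differs. The ratio is (1.5 + 1.5) / 2 = 1.5, the same as for a doubling on the PFF alone. The external comparison cannot tell these two situations apart. TAP laboratory events from Part 1, if included, would add further events unrelated to either foot.

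**3. What a within-participant comparison shows.** Count participants who had an event on one foot only (discordant). If the feet carry equal risk, each such participant falls on either side with probability 0.5. If all k are on one side, the exact two-sided p-value is 2 × 0.5^k.
- k = 5: 0.0625.
- k = 6: 0.031.
- k = 8: 0.008.
- A 7 to 1 split: 2 × (1 + 8) / 256 = 0.070.

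At least six discordant participants, all in one direction, are therefore needed for p < 0.05. These counts are illustrative. The unit must be the participant, because several falls in one person are not independent.

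**4. How much that comparison could detect.** Two-week risks are assumed and periods are taken as independent. Power is for an exact two-sided 0.05 test on discordant participants, 40 completers, found by exact enumeration and counting results in which the PFF is worse.

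| Standard of care | PFF | Expected participants with an event | Power |
|---|---|---|---|
| 2% | 6% | 0.8 vs 2.4 | 1.5% |
| 5% | 10% | 2 vs 4 | 4% |
| 5% | 15% | 2 vs 6 | 18% |
| 5% | 20% | 2 vs 8 | 39% |
| 10% | 20% | 4 vs 8 | 15% |
| 10% | 30% | 4 vs 12 | 50.5% |

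With 15 completers, power is below 10% in every one of these scenarios.

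**5. If no events are seen on a foot.** The one-sided 95% upper bound is 1 − 0.05^(1/n).
- n = 40: 7.2%.
- n = 15: 18.1%.

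**The case against.** The strongest reply is that the plan is being tested against a question it does not ask. Its stated target is the risk of the protocol as a whole. Both Part 2 feet are study-assigned and the participant's own foot is stored meanwhile, so a PFF versus standard-of-care contrast cancels any risk the two share. This stands. The standard-of-care period is not the control for overall protocol risk, and a reader who infers that the literature comparison is mistaken and should be replaced goes further than the documents allow.

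A reader might also infer that the plan will pool events and so hide a cluster on the PFF. The protocol describes a list of reports. It does not say that the device worn will be left out, and section 6.0 provides for problem-report forms and event logs. Section 5.5 also requires study procedures to be evaluated after each adverse event or unanticipated problem, with suspension while any changes are put in place. That review makes a missed cluster less likely. The dilution in step 2 therefore shows what would follow from a total over both feet; it does not show that such a total is planned.

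Third, the by-foot comparison has little power, as step 4 shows, so it could not settle the question either. This stands too, and it argues for a descriptive table with intervals rather than a test. It does not argue for leaving the events unattributed: a wide but concurrent randomised contrast still carries information about the PFF that the literature cannot give.

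Finally, equal exposure exists only in Part 2, is approximate, and can be upset by withdrawal. That is a reason to report person-weeks.

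**Conclusion.** The concern holds as a gap in the planned analysis. The only safety comparison named is external, it cannot isolate a PFF effect, and the randomised within-participant standard-of-care period is not used for safety anywhere in the protocol or SAP. The planned exposure is up to 80 person-weeks per foot, which assumes 40 completers and full two-week periods.

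The documents do not support saying that the plan makes a false statement about the PFF, that it would conceal PFF events, or that the added comparison would establish or exclude extra risk. All event rates used above are assumptions. The primary biomechanical comparisons are unaffected. The change is worth making because it costs little and gives the new foot its own event rate beside its comparator.

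**What to change.** In section 5.5, Risks and Risk Management, and in the SAP:
- Record the device worn at each event (TAP, PFF or standard-of-care foot).
- Add one table of falls and component failures by device, with person-weeks of exposure. Part 1 has no standard-of-care period, so TAP events are shown on their own.
- For Part 2, report the number of participants with at least one event on each foot, and the within-participant difference with an exact confidence interval, labelled descriptive. Participants who leave before wearing the second foot count in the table by device but not in the paired difference; state both denominators.
- Keep the literature comparison, and say that it addresses overall protocol risk, not PFF risk.

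The cost is one column in the event log and one table. If events have already been collected, their dates and the randomisation record should allow the device to be assigned afterwards. The drawback is few events and wide intervals, so the text should say that the table cannot by itself rule out added risk.

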5.6 Data Analysis

Specific Aim 1: Kinematic and kinetic data from the experiment will be analyzed to identify the peak transverse-plane moment of the straight and both directions of the circle walking trials at the five different coupling ratios (0, 1:6, 1:4, 1:3, and 1:2). This data will be processed (Visual3D; C-Motion, Germantown, MD) and aggregated using project specific software (Matlab; Mathworks, Natick, MA).

We hypothesize that:

H1.1: When walking in a straight line, there exists a coupling ratio that minimizes the peak transverse-plane moment.

H1.2: When circle walking with the prosthetic limb on the inside of the turn, there exists a coupling ratio that minimizes the peak transverse-plane moment.

H1.3: When circle walking with the prosthetic limb on the outside of the turn, there exists a coupling ratio that minimizes the peak transverse-plane moment.

The statistical analysis to test these hypotheses (H1.1, H1.2, and H1.3) will require three linear mixed effects regression analyses. These analyses will test for differences between the five coupling ratios across the three different ambulatory activities with random effects for subject and subject by coupling ratio interaction. The experiment-wise significance will be set a priori at an alpha level of $p<0.05$ and a Bonferroni adjustment will be applied for multiple comparisons. All analyses will be performed using existing software (R Foundation for Statistical Computing with lme4 and multcomp packages, Vienna, Austria). Exact p-values will be reported for each test.

We conducted an exploratory power analysis for hypothesis **H1.1:** The peak torque at the interface between the socket and the residual limb will be significantly different between a passive prosthesis that couples transverse-plane rotation with ankle dorsiflexion and the standardized study prosthesis. For this within-subject randomized crossover study design, we used recently analyzed data ($n=1$) to compare the effect of a coupling ratio of 0 with 1:2. The difference in peak socket torque was 19% between the two coupling ratios with a standard deviation of 17% between peaks. We calculated 98 percent power to find a significant difference between the test prostheses at $p<0.05$ for 15 subjects.

Satisfaction data from the experiment will be tabulated for straight and both directions of the circle walking trials at the five different coupling ratios (0, 1:6, 1:4, 1:3, and 1:2). This data will be processed and aggregated using project specific software (Matlab; Mathworks, Natick, MA).

We hypothesize that:

H2.1: When walking in a straight line, there exists a coupling ratio that maximizes satisfaction.

H2.2: When circle walking with the prosthetic limb on the inside of the turn, there exists a coupling ratio that maximizes satisfaction.

H2.3: When circle walking with the prosthetic limb on the outside of the turn, there exists a coupling ratio that maximizes satisfaction.

The statistical analysis to test these hypotheses (H2.1, H2.2, and H2.3) will require three Friedman analyses of variance (ANOVA). These analyses will test for differences between the five coupling ratios across the three different ambulatory activities. The experiment-wise significance will be set a priori at an alpha level of $p<0.05$ and a Bonferroni adjustment will be applied for multiple comparisons. All analyses will be performed using existing VA enterprise software (SPSS Statistics v22; IBM, Inc.). Exact p-values will be reported for each test.

The results of testing hypothesis 1 will be used to define the optimal coupling ratio. The coupling ratios (0, 1:6, 1:4, 1:3, and 1:2) will be placed in rank order and an evenly weighted rank average will be used to identify the coupling ratio that minimizes the transverse-plane moment. If this algorithm cannot distinguish between two or more coupling ratios, then a similar method will be used to rank the results from hypothesis 2. If neither algorithm can distinguish the optimal coupling ratio, then the investigative team will engage the clinical

team and use their experience to select a coupling ratio for use in specific aim 2. Please see our discussion of this issue in the potential problems section.

Specific Aim 2: Kinematic and kinetic data from the experiment will be analyzed to identify the peak transverse-plane moment and hip work while walking straight and in both directions of the circle walking trials while wearing the study prostheses. This data will be processed (Visual3D; C-Motion, Germantown, MD) and aggregated using project specific software (Matlab; Mathworks, Natick, MA).

We hypothesize that:

H3.1: When walking in a straight line, the peak transverse-plane moment will be significantly different between the Pivot-Flex Foot and the standard-of-care prosthesis.

H3.2: When circle walking with the prosthetic limb on the inside of the turn, the peak transverse-plane moment will be significantly different between the Pivot-Flex Foot and the standard-of-care prosthesis.

H3.3: When circle walking with the prosthetic limb on the outside of the turn, the peak transverse-plane moment will be significantly different between the Pivot-Flex Foot and the standard-of-care prosthesis.

H4.1: When walking in a straight line, the positive sagittal-plane work done at the hip joint will be significantly different between the Pivot-Flex Foot and the standard-of-care prosthesis.

H4.2: When circle walking (steady-state turning) with the prosthetic limb on the inside of the turn, the positive sagittal-plane work done at the hip joint will be significantly different between the Pivot-Flex Foot and the standard-of-care prosthesis.

H4.3: When circle walking (steady-state turning) with the prosthetic limb on the outside of the turn, the positive sagittal-plane work done at the hip joint will be significantly different between the Pivot-Flex Foot and the standard-of-care prosthesis.

Our interest in the positive sagittal-plane work done at the hip joint stems from the lack of propulsive power produced by passive prosthetic feet during ambulation by individuals with lower limb amputation. While energy storing and returning prosthetic feet can provide some propulsive assistance, the positive sagittal-plane ankle joint power and work produced is far below that provided by the ankle-foot musculature of the intact limb (e.g., [56, 57]).

Individuals with lower limb amputation compensate with greater sagittal-plane hip joint power and work, which is likely one of the reasons why they walk slower and at higher metabolic cost than their intact counterparts (e.g., [17, 58-60]). Our preliminary results with the TAP suggest that when the coupling ratio was increased: (1) prosthetic-side positive hip work may decrease during straight walking and prosthesis-on-the-outside during circle walking, and (2) prosthetic-side negative hip work may decrease during prosthesis-on-the-outside during circle walking. Both are desirable outcomes as they may reduce the biomechanical effort associated with walking.

The statistical analysis to test these hypotheses (H3.1, H3.2, H3.3, H4.1, H4.2, H4.3) will require six linear mixed effects regression analyses. These analyses will test for differences by

foot type (Pivot-Flex Foot or standard-of-care) with random effects for subject and subject by foot type interaction. The experiment-wise significance will be set a priori at an alpha level of $p<0.05$ and a Bonferroni adjustment will be applied for multiple comparisons. All analyses will be performed using existing software (R Foundation for Statistical Computing with lme4 and multcomp packages, Vienna, Austria). Exact p-values will be reported for each test.

An exploratory power analysis for peak transverse-plane moments was performed using mean values from Orendurff et al. [61] exerted by able bodied subjects performing a turning task. In Orendurff's study, subjects (n=10) completed a 270° turn around a one meter circle with a peak ankle rotational torque of 0.167 ± 0.011 Nm/kg for the inside limb. Assuming a 10% within-subject difference between study prostheses and that the standard deviations are like those of Orendurff's, there is over a 97% chance to find a significant difference between stiffness settings for 15 participants.

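### The 98% power stated for Part 1 is that of one unadjusted test with inputs from one person, not of the multiplicity-adjusted tests the plan specifies

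*Protocol*

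**What the plan says.** All the power statements are in protocol section 5.6.

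**Part 1 (Specific Aim 1).** The power paragraph is labelled exploratory and attached to H1.1. It describes the contrast as one between "a passive prosthesis that couples transverse-plane rotation with ankle dorsiflexion and the standardized study prosthesis", but the calculation is of something else: "we used recently analyzed data ($n=1$) to compare the effect of a coupling ratio of 0 with 1:2". The inputs are a 19% difference in peak socket torque, "with a standard deviation of 17% between peaks". The result is "We calculated 98 percent power to find a significant difference between the test prostheses at $p<0.05$ for 15 subjects".

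The analysis paragraph just before it plans three mixed models, one per walking activity, each comparing five coupling ratios "with random effects for subject and subject by coupling ratio interaction". It sets the error rate: "The experiment-wise significance will be set a priori at an alpha level of $p<0.05$ and a Bonferroni adjustment will be applied for multiple comparisons". It does not say which comparisons make up the Bonferroni family. The SAP analyses outcome by coupling ratio with an F-test and then uses Tukey's method for the pairs.

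**Part 2 (Specific Aim 2).** Six mixed models are planned, under the same experiment-wise rule. The power paragraph, also labelled exploratory, takes a peak ankle rotational torque of 0.167 ± 0.011 Nm/kg for the inside limb from a published study of 10 able-bodied people. "Assuming a 10% within-subject difference between study prostheses", and SDs like those in that study, it concludes that "there is over a 97% chance to find a significant difference between stiffness settings for 15 participants". That paragraph gives no alpha and no within-subject correlation.

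**The concern.** A power figure should describe the test that will be run. Here the plan tightens the significance level for multiplicity, and the Part 1 power sentence quotes plain 0.05. A reader cannot make the correction unaided, because the Bonferroni family is undefined and the SAP names a different adjustment.

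The SD raises a separate question. A spread between peaks in one person describes step-to-step or trial-to-trial noise. It holds no information on how the effect of the coupling ratio differs from person to person, yet the planned subject-by-ratio random effect counts that variation as error.

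At stake is how far these sentences can be relied on. They are the only power statements in the documents, and both are given for 15 participants.

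**Working it through.** **Method.** Two-sided power from the noncentral t distribution. Noncentrality = (difference / SD of difference) × √n. The critical value is the t quantile at 1 − α/2, or the studentized range quantile divided by √2 for Tukey.

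**Step 1: reproduce the Part 1 figure.** Difference 19, SD of difference 17, n = 15 (section 5.6).
- 19/17 = 1.118, and noncentrality = 1.118 × √15 = 4.329.
- With df = 14 and α = 0.05, the critical t is 2.145 and power is **98.0%** (stated: 98%).
- Other readings do not match: one-sided 99.3%, normal approximation 99.1%, SD of difference 17√2 81.2%, two groups of 15 84.0%.

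**Step 2: apply the planned adjustment.** The family is not stated, so three sizes are assumed: 3 (the activities), 10 (the pairs among five ratios, 5 × 4 / 2) and 30 (10 pairs × 3 activities). Two df bases are shown. The first is the 14 df that yields the stated 98%. The second is (5 − 1)(15 − 1) = 56 df, for a balanced five-ratio model with compound symmetry.

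| Level | Power, 14 df | Power, 56 df |
|---|---|---|
| 0.05, unadjusted | 98.0% | 98.9% |
| 0.05/3 | 93.0% | 96.6% |
| 0.05/10 | 81.7% | 91.4% |
| 0.05/30 | 66.4% | 84.0% |
| Tukey, five ratios | 86.3% | 92.9% |

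The critical t for Tukey is 3.116 on 14 df and 2.819 on 56 df. Moving from 14 to 56 df raises power by itself, so adjusted and unadjusted figures should be compared within a column.

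**Step 3: sensitivity to the single-person SD** (14 df, n = 15, difference 19%). The SDs of 20% and 25% are illustrations; the documents give only 17%.

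| SD of difference | 0.05 | 0.05/3 | 0.05/10 | 0.05/30 |
|---|---|---|---|---|
| 17% | 98.0% | 93.0% | 81.7% | 66.4% |
| 20% | 92.7% | 81.6% | 63.8% | 46.0% |
| 25% | 78.1% | 59.8% | 39.4% | 24.2% |

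**Step 4: Part 2.** Difference = 10% of 0.167 = 0.0167 Nm/kg. SD of difference = 0.011 × √(2(1 − r)), where r is the within-subject correlation (not given). n = 15, df = 14. The family of six (H3.1–H3.3 and H4.1–H4.3) is an assumption.

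| r | SD of difference | Power at 0.05 | Power at 0.05/6 |
|---|---|---|---|
| 0 | 0.0156 | 97.1% | 83.9% |
| 0.25 | 0.0135 | 99.4% | 93.9% |
| 0.36 | 0.0124 | 99.8% | 97.0% |
| 0.5 | 0.0110 | 99.98% | 99.3% |

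The row r = 0 at 0.05 is a close match to the stated figure. Two independent groups of 15 with SD 0.011 would give 98.0% at 0.05, which also fits, but the planned comparison is within-subject.

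**The case against.** The strongest reply is that little is hidden. The Part 1 paragraph itself discloses the ratio contrast, the single participant, the 0.05 level, the 15 subjects and the exploratory status. The coupling ratio carried into Part 2 is chosen by rank average, not by a significance test, and up to 40 people may be enrolled in each part. All of that stands, and it is why the point is minor. It does not make 98% the power of the planned tests.

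A second reply concerns Part 2. A reader might infer that its figure, too, has been shown to ignore the adjustment. The documents do not support that. No alpha is stated, the figure is a lower bound, and it survives a 0.05/6 level if the within-subject correlation is about 0.36 or more. The unadjusted reading is an inference from the close match at zero correlation.

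Two further inferences are tempting, in opposite directions. One is that the trial is underpowered. The variation in the ratio effect between people is not given, and averaging over the several walks planned per setting would reduce the within-person noise, so the net effect of the single-person SD on power cannot be computed. The other is that enrolling 40 settles the matter. With the stated inputs power at 40 is close to 100%, but that rests on the same SD from one person. With an illustrative SD of 30%, power at n = 40 and 0.05/30 is about 73% (39 df) to 79% (156 df). Forty is also a ceiling in the abstract, and the SAP cites a small sample size as one reason for not testing satisfaction.

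**Conclusion.** Wrong as written for Part 1; minor. The stated 98% is the power of one unadjusted paired test. On the same inputs and the same 14 df, the adjusted tests have 66% to 93% power, depending on the Bonferroni family, or 86% under Tukey. With 56 error df the range is 84% to 97%, still below 98% under every adjustment tried. Whether power stays above 80% at 15 subjects therefore depends on the df basis and the family: it does in every case with 56 df, but not on 14 df over 30 comparisons.

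These figures assume that 17% is the SD of the paired difference, which is the reading that reproduces 98%. Since that SD comes from one person, the margin is uncertain: at an SD of 25% even the unadjusted 14-df power is 78%.

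For Part 2 the finding is one of incomplete reporting, not of a demonstrated error. Power at 0.05/6 is 84%, 94% or 99% for correlations of 0, 0.25 or 0.5. The description of the contrast is also wrong in both parts. The Part 1 text names two prostheses but computes two ratio settings, and the Part 2 text speaks of stiffness settings although the hypotheses compare two feet.

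**What to change.** Reword a few sentences in protocol section 5.6.

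**Part 1**
- State which comparisons form the Bonferroni family, and reconcile Bonferroni in the protocol with Tukey in the SAP, so that one adjustment applies.
- Restate the power for 15 participants at that adjusted level, with its df basis, using the matching entry from the Step 2 table.
- Describe the contrast as coupling ratio 0 against 1:2 in straight walking.
- Say that the 19% and 17% come from one participant and exclude between-person variation in the effect, and show power for larger SDs, as in Step 3.

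**Part 2**
- State the alpha and the within-subject correlation assumed, or give power over a range of correlations, as in Step 4.
- Say that the mean and SD are ankle torque in able-bodied people.
- Name the contrast as the Pivot-Flex Foot against the standard-of-care foot with the prosthetic limb on the inside of the turn (H3.2).

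Do not add a reassurance that power exceeds 99% at 40 per part, because for Part 1 it would rest on the single-person SD.

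The cost is a less favourable stated power for 15 participants. Enrolment, visits and planned models do not change; the only analysis decision needed is which multiplicity adjustment is meant.
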